5.5.2 Dose-Reduction Steps

Dose-reduction steps are below:

Table 1: Pomalidomide Dose Reduction Steps for Phase I and II				
Starting Dose	MTD (as determined in Phase I portion) mg daily on Days 1-28 every 28 days			
Dose Level – 1	Decrease by 1 mg daily from MTD on Days 1-21 every 28 days*			
Dose Level – 2	Decrease by 2 mg daily from MTD on Days 1-21 every 28 days*			
Dose Level – 3	Decrease by 3 mg daily from MTD on Days 1-21 every 28 days*			

* Pomalidomide dosing for Phase I cohorts 1 and 2 given on days 1-28 of a 28-day cycle and changed to Days 1-21 of a 28 day cycle with Cohort 3.

Table 2: DEXAMETHASONE Dose Reduction Steps for Phase I and II		
Starting Dose 20 mg QD once weekly every 28 days		
Dose Level –1	10 mg QD once weekly every 28 days	
Dose Level –2	4 mg QD once weekly every 28 days	

Pomalidomide	Page 27 of 66 Protocol:

Dosing will be adjusted as needed by study investigators as outlined in the tables in Section 5.5.3. If dexamethasone is permanently discontinued, the patient will continue with single agent Pomalidomide.

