5.1 Overall design

STUDY DESIGN:

Phase I/II dose-escalation study of pomalidomide and dexamethasone in persons with previously-treated AL-amyloidosis. During the Phase I portion the MTD will be determined based on DLT in the first cycle. At the MTD an expanded cohort of 12 subjects will be evaluated to estimate efficacy.

The study includes a screening period, a treatment (dose escalation) period, and a follow-up period for survival. After giving written informed consent, subjects will be evaluated for eligibility for enrollment in the study and baseline evaluations will be performed. Subjects who satisfy all inclusion and exclusion criteria will begin study drug treatment with dose escalation. Standard dose escalation rules will be used.

Subjects will be monitored every cycle for safety, hematological status, and organ function during therapy or until the occurrence of progressive disease (PD).

Treatment Group Assignments and Subject Replacement

This is a dose-escalation study and dose escalation will proceed through 3 dose-levels according to standard rules in which dose levels are started sequentially after complete evaluation of the occurrence of DLT. Based on the dose escalation scheme, as many as 30 subjects could be enrolled in the study. Subjects who discontinue pomalidomide for reasons other than DLT before completing at least 2 treatment cycles are to be replaced.

Subpopulations

An additional 12 subjects will be enrolled in an expanded cohort for analysis of efficacy at each schedule studied.

Subjects in this cohort will be treated at the dose defined as the MTD for that schedule.

Pomalidomide

Schema:

Phase I:

Pomalidomide 2 mg/day D1-21 – dose escalation to 4 mg/day by 1 mg units* Dexamethasone 10-20 mg D1, 8, 15, 22

* Pomalidomide dosing for Phase I cohorts 1 and 2 given on days 1-28 of a 28-day cycle and changed to Days 1-21 of a 28 day cycle with Cohort 3.

This cycle will be repeated every 28 days.

Subjects will take aspirin 325 mg/day to prevent venous thrombosis whilst on-study. A proton pump inhibitor will be used for GI prophylaxis.

Phase II:

Pomalidomide [MTD] mg/day D1-21 Dexamethasone 10-20 mg D1, 8, 15, 22

This cycle will be repeated every 28 days.

Subjects will take aspirin 325 mg/day for prophylaxis against venous thrombosis while on study. A proton pump inhibitor will be used for GI prophylaxis.

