5.4.2 Dosing regimen

The initial planned dose of pomalidomide for investigation is 2 mg/day, orally on days 1 - 21 (28 day cycle).* Dosing will be in the evening at approximately the same time each day,

either 2 hours before or 2 hours after food ingestion. Participants will be instructed to avoid smoking, as smoking can decrease the efficacy of pomalidomide. Only enough pomalidomide for one cycle of therapy will be supplied to the subject each cycle.

* Pomalidomide dosing for Phase I cohorts 1 and 2 given on days 1-28 of a 28-day cycle and changed to Days 1-21 of a 28 day cycle with Cohort 3.

The planned dose levels of Pomalidomide are presented below in Table 15-1 table.

		Enrollment (Number of Subjects)					
Dose Group	Pomalidomide Dose (mg/dose)	Initial	Expanded at MTD ^a				
1	2	3 ^b	3				
2	3	3	3	12			
3	4	3	3				

Table 15-1 Planned Study Drug Doses

a. Twelve additional subjects are to be enrolled in an expanded cohort for analysis of efficacy and treated at the MTD for each dosing schedule.

b. If the first 2 subjects enrolled experience DLT then this cohort is closed and further subjects will be evaluated at 1mg/day dose and the cohort expanded at that dose.

The dose escalation rules will follow the standard Fibonacci method.

Dose escalation algorithm

At least 3 subjects are to be enrolled in each dose group, beginning with the 2 mg/dose. Within each dose group, 3 subjects are to complete at least 2 treatment cycles. It is noted that if the first 2 subjects in the first cohort develop DLT, then the cohort at the 1 mg/dose dose will be defined as the MTD.

Dose escalation within a cohort is not allowed.

- If after all 3 subjects complete 1 treatment cycle:
 - No subject experiences DLT, then enrollment at the next planned dose level may commence.
 - One subject experiences DLT, then 3 additional subjects are to be enrolled at the current dose level.
 - If 1 of 6 subjects experiences DLT, then enrollment at the next planned dose level may commence.
 - If 2 or more of 6 subjects experience DLT, then the previous dose is declared the MTD.

Two or more subjects experience DLT, then the previous dose is declared the MTD.

- Dose escalation continues through the 3 dose levels in order to define the MTD based on the occurrence of DLT in the first cycle. Definitions of DLT and MTD are as follows:

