5.5.1 Dose-Modification Guidelines

During the study, the focus of the evaluations is on the assessment of toxicity to document the occurrence of DLT. Although DLTs may occur at any point during treatment, only DLTs occurring during Cycle 1 of treatment must influence decisions regarding doseescalation, expansion of a dose level, or evaluation of intermediate dose levels. However, DLTs occurring in later cycles may be taken into consideration for dose-escalation decisions, at the discretion of the investigators. Unless a DLT is documented to have occurred, no dose modification is allowed during Cycle 1.

In the event that a patient experiences DLT during Cycle 1, treatment should be held and the event will be counted toward the assessment of MTD for the given cohort. Patients experiencing DLTs in Cycle 1 may be restarted following recovery from toxicity at the discretion of the investigator according to the guidelines provided in Section 5.5.2. If a decision is made to restart study therapy following a DLT, the pomalidomide dose must be reduced 1 dose level. The patient will be evaluated weekly for possible toxicities that may have occurred after the previous dose(s). If multiple toxicities are noted, the dose adjustments and/or delays should be made according to the most severe toxicity guidelines.

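### Table 1 counts pomalidomide reductions down from the MTD, so it cannot be evaluated before the MTD is declared, and at least one step is zero or negative at every MTD of 3 mg or less

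*Combined protocol and SAP*

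**What the plan says.** Table 1 in Section 5.5.2 is titled "Pomalidomide Dose Reduction Steps for Phase I and II". Its starting row is "MTD (as determined in Phase I portion) mg daily on Days 1-28 every 28 days". The three levels below it are "Decrease by 1 mg daily from MTD on Days 1-21 every 28 days", "Decrease by 2 mg daily from MTD on Days 1-21 every 28 days" and "Decrease by 3 mg daily from MTD on Days 1-21 every 28 days".

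Section 5.5.1 deals with a DLT in Cycle 1. It allows treatment to restart after recovery under the guidelines of Section 5.5.2, and adds: "If a decision is made to restart study therapy following a DLT, the pomalidomide dose must be reduced 1 dose level".

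The candidate doses come from two places. Section 5.1 gives a start at 2 mg/day with "dose escalation to 4 mg/day by 1 mg units", which matches the 2, 3 and 4 mg groups of Table 15-1. Section 5.4.2 adds a fallback if the first two subjects of the first cohort have DLTs: "then the cohort at the 1 mg/dose dose will be defined as the MTD".

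Section 5.4.1 lets Phase I patients still on treatment when the MTD is defined stay on their current dose. Table 3 in Section 5.5.4 tells the investigator, for several toxicities, to restart one level down. Section 5.5.3 says that a subject whose pomalidomide is stopped permanently leaves the study, but does not link this to running out of dose levels.

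**The concern.** A reduction table needs a reference dose that exists when the table is used. Table 1 takes the MTD, which is the result of Phase I, and applies it to subjects treated during Phase I. It also subtracts fixed amounts from a quantity that may be as small as the amounts themselves, without a floor.

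What is at stake is the dose given after a toxicity. Followed to the letter, the table gives no dose during escalation, and a zero or negative dose for some MTDs. For some Phase I subjects still on treatment after the MTD is declared, it gives a dose no lower than the one that they were taking.

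**Working it through.** The documents state no resulting doses in mg, so there is no figure to reproduce. The check applies Table 1 literally.

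**Inputs**
- Reference dose: the MTD (Table 1, starting row).
- Steps: k = 1, 2, 3 mg below the MTD (Table 1).
- Possible MTDs: 2, 3 and 4 mg (Section 5.1, Table 15-1), and 1 mg by the fallback (Section 5.4.2).
- Smallest capsule: 1 mg (Section 5.1.1.5).

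**Step 1. Levels by MTD.** Level -k = MTD - k.

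| MTD (mg) | Level -1 | Level -2 | Level -3 | Steps of at least 1 mg |
|---|---|---|---|---|
| 4 | 4 - 1 = 3 | 4 - 2 = 2 | 4 - 3 = 1 | 3 of 3 |
| 3 | 3 - 1 = 2 | 3 - 2 = 1 | 3 - 3 = 0 | 2 of 3 |
| 2 | 2 - 1 = 1 | 2 - 2 = 0 | 2 - 3 = -1 | 1 of 3 |
| 1 | 1 - 1 = 0 | 1 - 2 = -1 | 1 - 3 = -2 | 0 of 3 |

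At an MTD of 3 mg only the last step fails, and it is zero. Negative values arise only at 2 mg or less. All three steps fail only at the 1 mg fallback. Across MTDs of 2 and 3 mg, three of the six steps are positive and three are zero or negative.

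**Step 2. Before the MTD is declared.** Section 5.4.2 derives the MTD from first-cycle DLTs. A Phase I subject restarting after a Cycle 1 DLT during escalation is sent to a table whose reference dose is not yet known, so MTD - k has no value. The same holds for a later-cycle toxicity handled under Table 3 while escalation continues.

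**Step 3. After the MTD is declared.** For a Phase I subject who stays on own dose d under Section 5.4.1, Level -k is a real reduction only if 1 ≤ MTD - k < d.

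- d = 2, MTD = 4: levels 3 (higher), 2 (unchanged), 1 (a reduction).
- d = 3, MTD = 4: levels 3 (unchanged), 2 and 1 (reductions).
- d = 2, MTD = 3: levels 2 (unchanged), 1 (a reduction), 0.
- d = 4, MTD = 3: levels 2 and 1 (reductions), 0.

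The first case conflicts directly with Table 3, which requires a restart one level lower: the literal first step moves the subject from 2 to 3 mg.

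**The case against.** The strongest reply is that the protocol does give a workable instruction. Section 5.5.1 requires a reduction of one level, Table 3 speaks of going one level down, and Table 15-1 with its footnote lists 4, 3, 2 and 1 mg. Together these imply a ladder from the subject's own dose. This stands as a reason not to say that investigators have no instruction. It does not clear the table, which covers both phases and counts from the MTD, so the implied ladder contradicts the wording of the table to which subjects are sent.

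A reader might infer that Phase I subjects never have a usable level. The documents do not support that: once the MTD is known, many subjects still on treatment have one or more real reductions (Step 3).

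A reader might also infer that a 2 mg subject with a Cycle 1 DLT would be restarted at 3 mg. The timing does not fit. Dose levels open in sequence after DLT evaluation (Section 5.1), so an MTD of 4 mg would not be known at that restart. The 3 mg example applies to a later toxicity in a subject who kept 2 mg.

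The lowest MTDs may no longer be reachable. The schedule footnote describes cohorts 1 and 2 as already dosed. If Cohort 3 is the 4 mg group, which the documents do not state, the escalation rules leave only 3 or 4 mg, and the only zero step is Level -3 at 3 mg. That narrows Step 1 but leaves the rest.

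Finally, disease evaluations take place at one centre with weekly review (Sections 5.1 and 9.2), which makes a literal misreading less likely. That is a fair mitigation, but it does not correct the text.

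**Conclusion.** The point holds in a limited form. Table 1 is wrong as written in three ways: it is undefined for Phase I subjects until the MTD is declared; it gives one, two or three zero or negative steps at MTDs of 3, 2 and 1 mg, with no floor; and after an MTD of 4 mg it gives a Phase I subject still on 2 mg a first step of 3 mg and a second of 2 mg.

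This rests on reading Table 1 literally and on the MTDs that the protocol itself allows. It is not a claim that every step fails or that no reduction instruction exists.

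The reach is limited. A Cycle 1 DLT counts toward the MTD whatever dose is used at restart, so the MTD determination and the planned analyses do not depend on Table 1. The point matters for subject safety and for consistent dosing after toxicity, and should be corrected.

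**What to change.** Reconcile Table 1 in Section 5.5.2 with Section 5.4.1 (patients who stay on their current dose), Section 5.4.2 and Table 15-1 (the planned levels and the 1 mg fallback), Section 5.5.1 (restart after a DLT), and Sections 5.5.3 and 5.5.4 (starting a new cycle, and Table 3). Two things need to come out of this:

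- The reference dose for a reduction is the same in all these places and can be evaluated in both phases, including before the MTD is declared.
- Table 1 states what applies when a step would reach zero or less.

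Which reference dose and which rule to adopt is a clinical decision for the investigators, and none is proposed here.

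The cost is table wording and matching cross-references, handled as an amendment under Section 8.1. The sample size, DLT definition, escalation rules and analyses do not change.

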5.5.3 Instructions for initiation of a New Cycle

A new course of treatment may begin on the scheduled Day 1 of a new cycle if:

- The ANC is \geq **1,000**/mm³;
- The platelet count is \geq 50,000/mm³;
- Any pomalidomide-related rash, neuropathy or cardiac event that may have occurred has resolved to ≤ grade 1 severity;
- Any other pomalidomide-related adverse events that may have occurred have resolved to \leq grade 2 severity.

If these conditions are not met on Day 1 of a new cycle, the subject will be evaluated weekly and a new cycle of treatment will not be initiated until the toxicity has resolved as described above. If pomalidomide dosing was held during the previous cycle and was restarted with a one-level dose reduction without requiring an interruption for the remainder of the cycle, then that reduced dose level will be initiated on Day 1 of the new cycle. If **pomalidomide dosing was omitted due to an attributable toxicity (see table 3) for the remainder of the previous cycle or if the new cycle is delayed due to attributable toxicity newly encountered on the scheduled Day 1, then the new cycle will be started with a one-level dose reduction of pomalidomide. If pomalidomide is permanently discontinued, the subject will be removed from study. If dexamethasone is permanently discontinued, the subject may continue on single-agent pomalidomide.**

5.5.4 Instructions for dose modifications or interruptions during a cycle.

Table 3: Pomalidomide Dose Modifications for toxicities attributable to Pomalidomide			
NCI CTCAE Toxicity Grade	Onset Day 2-14 of Cycle	Onset ≥ Day 15 of Cycle	
Grade 3 neutropenia associated with fever (temperature ≥ 38.5º C) or Grade 4 neutropenia ¥	 Hold (interrupt) pomalidomide dose. Follow CBC weekly. If neutropenia has resolved to ≤ grade 2 prior to Day 21, restart pomalidomide at next lower dose level and continue the cycle. If neutropenia is the only toxicity for which a dose reduction is required. G-CSF may be used and the pomalidomide dose maintained ¥ 	 Omit pomalidomide for remainder of cycle See Instructions for Initiation of a New Cycle and reduce the dose of pomalidomide by 1 dose level. If neutropenia is the only toxicity for which a dose reduction is required. G-CSF may be used and the pomalidomide dose maintained for the next cycle at the investigators discretion.¥ 	
Thrombocytopenia ≥Grade 3 (platelet count < 50,000/mm³)	 Hold (interrupt) pomalidomide dose. Follow CBC weekly Hold prophylactic anticoagulation for thrombocytopenia (grade 3 or 4) or bleeding. Prophylactic anticoagulation can be resumed when platelet count ≥50k (≤2 grade) and no sign of bleeding. If thrombocytopenia resolves to ≤ grade 2 prior to Day 21, restart pomalidomide at next lower dose level and continue the cycle. 	 Omit pomalidomide for remainder of cycle See Instructions for Initiation of a New Cycle and reduce the dose of pomalidomide by 1 dose level. Hold prophylactic anticoagulation for thrombocytopenia (grade 3 or 4) or bleeding. Prophylactic anticoagulation can be resumed when platelet count ≥50k (≤2 grade) and no sign of bleeding. 	
Non-blistering rash Grade 3 Grade 4	 If Grade 3, hold (interrupt) pomalidomide dose. Follow weekly. If the toxicity resolves to ≤ grade 1 prior to Day 21, restart pomalidomide at next lower dose level and continue the cycle. 	 Omit pomalidomide for remainder of cycle. See Instructions for Initiation of a New Cycle and reduce the dose of pomalidomide by 1 dose level. Discontinue pomalidomide. Remove subject from study. 	
	Discontinue pomalidomide. Remove subject from study.		
Desquamating (blistering) rash- any Grade	Discontinue pomalidomide. Remove subject from study.	Discontinue pomalidomide. Remove subject from study.	
Neuropathy Grade 3	 Hold (interrupt) pomalidomide dose. Follow at least weekly. If the toxicity resolves to ≤ grade 1 prior to Day 21, restart pomalidomide at next lower dose level and continue the cycle. 	 Omit pomalidomide for the remainder of the cycle. See Instructions for Initiation of a New Cycle and reduce the dose of pomalidomide by 1 dose level. 	
Grade 4	 Discontinue pomalidomide. Remove subject from study. 	Discontinue pomalidomide. Remove subject from study.	

Pomalidomide

Table 3: Pomalidomide Dose Modifications for toxicities attributable to Pomalidomide			
NCI CTCAE Toxicity Grade	Onset Day 2-14 of Cycle	Onset ≥ Day 15 of Cycle	
Venous thrombosis/embolism ≥ Grade 3	 Hold (interrupt) pomalidomide and start anticoagulation; restart pomalidomide at investigator's discretion (maintain dose level). 	Omit pomalidomide for remainder of cycle. See Anticoagulation Consideration (Section 5.6.1.2)	
other non-hematologic toxicity ≥ Grade 3	 Hold (interrupt) pomalidomide dose. Follow at least weekly. If the toxicity resolves to ≤ grade 2 prior to Day 21, restart pomalidomide at next lower dose level and continue the cycle. 	 Omit pomalidomide for remainder of cycle. See Instructions for Initiation of a New Cycle and reduce the dose of pomalidomide by 1 dose level. 	
Hyperthyroidism or hypothyroidism ≥ Grade 2	 Omit pomalidomide for remainder of cycle, evaluate etiology, and initiate appropriate therapy. If the toxicity resolves to ≤ grade 1 prior to Day 21, restart pomalidomide at next lower dose level and continue the cycle. 	 Omit pomalidomide for remainder of cycle, evaluate etiology, and initiate appropriate therapy. See Instructions for Initiation of a New Cycle and reduce the dose of pomalidomide by 1 dose level. 	
Any attributable or non- attributable hospitalization or toxicity grade < 2	 Pomalidomide may be held or continued at the discretion of the treating investigator. Once resumed, maintain dose level. 	 Pomalidomide may be held or continued at the discretion of the treating investigator. If held, see Instructions for Initiation of a New Cycle and maintain dose level. 	

¥ As stated in the table, pomalidomide should be held for occurrence of grade 3 neutropenia with fever or grade 4 neutropenia attributable to Pomalidomide. Follow CBC weekly.

If neutropenia has resolved to \leq grade 2 prior to Day 21, restart pomalidomide at next lower dose level and continue the cycle. If neutropenia is the only toxicity for which a dose reduction is required, G-CSF may be used and the pomalidomide dose can be maintained. In case of second occurrences of Grade 4 neutropenia or Grade 3 neutropenia with fever in the setting of GCSF, pomalidomide will be held and if neutropenia has resolved to \leq grade 2 prior to Day 21, restart pomalidomide at next lower dose level with addition of G-CSF

Table 4: Non-hematological toxicity attributable to dexamethasone			
	Grade 1-2	Grade 3-4	
Dyspepsia / Gl	Start H2-blocker or Proton Pump Inhibitor if not already on one of these.	Hold dexamethasone and start H2- blocker or Proton Pump Inhibitor if not already on one of these. Once toxicity has decreased to Grade 0-2, resume Dex at one dosing level lower with continued H2B or PPI. If Grade 3-4 toxicity persists for more than 14	

Dose Modifications for Dexamethasone

		days,endoscopy or other UGI
		evaluation is encouraged.
Edema	May add diuretic	Decrease dex by one dosing level, and
		add diuretics
Confusion/Mood Alteration	For Grade 2, decrease	Hold dex until severity decreases to
	dexamethasone by one dosing	Grade 0-2, then resume dex at next
	level without holding dose	lower dosing level.
Myopathy	For Grade 2-4, decrease dexamethasone by one dosing level without	
	holding dose	
Hyperglycemia	For Grade 2, add oral	Add oral hypoglycemic agents and/or
	hypoglycemic agents and/or	Insulin, and decrease dosing level by
	insulin to control blood sugar. If	one.
	hyperglycemia not able to be	
	easily controlled, decrease	
	dexamethasone by one dosing	
	level without holding dose.	
Other	For Grade 2, decrease	Hold dex until severity decreases to
	dexamethasone by one dosing	Grade 0-2, then resume dex at next
	level without holding dose	lower
	_	

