• relationship of changes in the levels of the biomarkers BNP and troponin I compared to frequency of specific adverse events and the occurrence of DLT

STUDY DURATION: Treatment may continue until subject experiences unacceptable toxicities or disease progression. Follow-up will take place every 3 months until disease progression, then annually for survival. Accrual ~24 months	TOTAL SAMPLE SIZE: 30 subjects
DOSING REGIMEN(S):	STUDY DRUG SUPPLIES:
Phase I portion:	Celgene Corporation will
Pomalidomide 2 mg/day D1-21 – dose escalation to 4 mg/day in 1 mg increments in phase I* Dexamethasone 10-20 mg D1, 8, 15, 22 The above cycle will be repeated every 28 days. * Pomalidomide dosing for Phase I cohorts 1 and 2 given on days 1- 28 of a 28-day cycle and changed to Days 1-21 of a 28 day cycle with Cohort 3.	supply pomalidomide as 1.0 mg and 2.0 mg
Phase II portion:	
Pomalidomide [MTD] mg/day D1-28 Dexamethasone 10-20 mg D1, 8, 15, 22	
This cycle will be repeated every 28 days.	

Protocol

2 Schedule of Study Assessments *

Pre-Study Cycle One*		Cycle One*			Cycles 2, 3	Cycles* 5, 6, 8, 9, 11, 12	Cycles* 4, 7 and 10 ∞	*30 days of discontinuation From Study Drug	Follow-Up ⁸ Phase	
		Day 1	Day 8 §	Day 15	Day 22 §	Day 1	Day 1	Day 1		Every 3 months
Physical examination, vital signs, weight	х	х			х	Х		Х	х	х
SWOG performance status	Х	Х			Х	Х		Х	Х	Х
CBC with differential	Х	Х	X ⁶	X ⁶	X ⁶	X ⁶	X ⁶	Х		Х
Pregnancy test ²	X ^{2, 3}	X ³	X ³	X ³	X ³	X ³	X ³	X ³	X ³	
Education and counseling guidance ⁷		X 7				X ⁷	X ⁷	X ⁷		
Sodium, chloride, CO2, Glucose	Х	Х	х	х	х	Х	х			х
BUN, creatinine, potassium, Magnesium, phosphorous	х	х	х	х	х	х	х	х		х
ALT, AST, albumin, alk phos, bilirubin	х	х				Х	x			х
calcium	Х	Х				Х	Х	Х		Х
Cholesterol, triglyceride, TSH	х							Х		х
Total Protein, LDH, INR, PTT	x	х						Х		х
BNP, uric acid	Х	Х	Х	Х	Х	Х	Х	Х		Х
C-reactive protein, Beta 2- microglobulin	х							Х		х
IgG, IgA, IgM	Х							Х		Х
Serum immunofixation electrophoresis	x							Х		х
Urine immunofixation electrophoresis	х							Х		х
24 hour urine protein	Х							Х		Х
Free light chain assay	Х					Х	Х	Х		Х
Bone marrow biopsy and aspirate	х							X ⁵		X ⁵
EKG	Х							Х		Х
ECHO	Х							X ⁵		X ⁵
CXR	Х							X ⁵		X ⁵
Urinalysis	Х							Х		Х

Dispensement of Cycle 1		V								
study drug		^								
Record adverse events			Х	Х	Х	Х	Х	Х	Х	
Record concomitant therapies/procedures		х				Х	Х	Х	х	
Dispense study drug for next cycle		х				х	Х	Х		
Perform drug accountability		х				х	Х	Х	х	

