5.3 Visit schedule and assessments

Screening Assessments and all on study scheduled visits and assessments are outlined in Section 2 Table of Study Assessments.

At treatment discontinuation, subjects will undergo off study evaluations per the Schedule of Assessments, Section 2. In addition, a safety assessment will be done approximately 30 days post the last dose of study drug. Follow-Up contact with the subjects should occur at a minimum of every 3 months until progression, then annually.

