5.8 Follow-Up

Subjects who discontinue treatment for any reason, will be followed every 3 months until disease progression, then annually for survival, as clinically indicated. At treatment discontinuation, subjects will undergo a safety assessment approximately 30 days post the last dose of study drug. In addition off study evaluations per the Schedule of Assessments, Section 2 will be done.

6 Adverse events

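### On permanent stop of pomalidomide, Section 5.5.3 (and Table 3 for three toxicities) removes the subject from the study while Section 5.8 requires follow-up, and the text does not reconcile them

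*Combined protocol and SAP*

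**What the plan says.** **Removal.** Section 5.5.3 (initiation of a new cycle) states: "If pomalidomide is permanently discontinued, the subject will be removed from study". The sentence carries no exception for follow-up and is not limited to toxicity. Table 3 in Section 5.5.4 gives the instruction "Discontinue pomalidomide. Remove subject from study" for grade 4 non-blistering rash, desquamating rash of any grade and grade 4 neuropathy. Its other rows hold, omit, reduce or continue the drug.

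**Follow-up.** Section 5.8 states: "Subjects who discontinue treatment for any reason, will be followed every 3 months until disease progression, then annually for survival". Section 5.3 agrees: "Follow-Up contact with the subjects should occur at a minimum of every 3 months until progression, then annually". So does the synopsis: "Follow-up will take place every 3 months until disease progression, then annually for survival".

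**Qualifiers.** The Section 5.8 sentence ends "disease progression, then annually for survival, as clinically indicated", and the text does not show whether the last three words limit the annual contact or the whole schedule. Footnote 8 of the schedule of assessments ties the three-monthly examinations to responders.

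**Use of the data.** Response duration, time-to-event and survival are secondary endpoints (Sections 4.1.2 and 4.2.2). Section 10.3 plans descriptive analyses of time to and duration of hematologic response and of time to worsening. It gives no censoring rule and rules out imputation.

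**The concern.** Stopping treatment and leaving the study are different events, and the protocol uses wording for the first that can be taken as the second. If staff act on 5.5.3 or Table 3 as written, observation ends on the day pomalidomide is stopped for good. Such a subject still contributes time up to that day. What is lost is any later progression, organ worsening or death.

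A stop for severe toxicity may be related to prognosis, so censoring at that moment may be informative. Section 10.3 has no rule that would limit the effect. Missed follow-up is also hard to recover afterwards, so the wording is best settled before it is applied.

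**Working it through.** The plan states no figure on this point, so the check is mainly a comparison of text.

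**1. Passages side by side**

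| Question | Section 5.5.3 and Table 3 | Sections 5.3, 5.8 and synopsis |
|---|---|---|
| Trigger | Permanent stop of pomalidomide (5.5.3); three named toxicities (Table 3) | Stopping treatment for whatever reason (5.8) |
| Consequence | Removal from the study | Three-monthly follow-up to progression, then annual |
| Exception or cross-reference to the other rule | None | None |

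The triggers overlap: every permanent stop of pomalidomide under 5.5.3 is also a treatment discontinuation under 5.8. No passage defines removal from study or says which rule takes precedence.

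**2. Which reading is likelier?** Section 5.3 says "At treatment discontinuation, subjects will undergo off study evaluations per the Schedule of Assessments, Section 2" and, in the same paragraph, requires continued contact. There, being off study plainly coincides with the start of follow-up. Section 5.7 lists progression among the events that end treatment. If every permanent stop meant leaving the study, the annual survival follow-up after progression would have almost nobody left to apply to. Both points favour removal from treatment. On the other side, Section 5.7 is headed as discontinuation of treatment and does not mention removal from study. Section 10.3 speaks of withdrawal from the study and attaches an analytic consequence, exclusion of replaced subjects from the MTD analysis. The literal reading therefore remains available.

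**3. How many subjects might be touched?** For illustration only, take the 20% toxicity-stop rate that Section 3.3 reports for lenalidomide.
- Efficacy population of 12 (Section 10.3): 12 × 0.20 = 2.4 expected; chance of at least one = 1 − 0.80^12 = 0.93.
- The 18 subjects at the MTD used for the precision statement: 18 × 0.20 = 3.6 expected; chance of at least one = 1 − 0.80^18 = 0.98.

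The rate comes from another drug and counts toxicity stops only, whereas the 5.5.3 sentence covers all permanent stops.

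**4. Can a bias be derived?** Let f be the fraction removed, s their true one-year survival, and x the one-year survival of the others. Take overall one-year survival as 77%, the figure Section 3.2 reports for pomalidomide in AL amyloidosis. In the limiting case where removal is very early:

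f·s + (1 − f)·x = 0.77, so x − 0.77 = f(0.77 − s)/(1 − f).

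With f = 0.20 this is 0.25 × (0.77 − s):

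| s | Status of s | x | Shift (points) |
|---|---|---|---|
| 0.50 | assumed | 0.8375 | +6.75 |
| 0.60 | assumed | 0.8125 | +4.25 |
| 0.77 | same as overall | 0.77 | 0 |
| 0 | lower bound | 0.9625 | +19.25 |
| 1 | upper bound | 0.7125 | −5.75 |

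The documents give no value for s. Even granting 20% and 77%, the shift could lie anywhere from −5.75 to +19.25 points, and its sign depends on s. Removal later in the year would make it smaller.

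**5. Sampling error for comparison.** At 77%, √(0.77 × 0.23/18) = 0.099, about 10 points for 18 subjects.

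**6. Primary endpoint.** DLT is assessed in cycle 1 only, and Section 5.5.1 counts a cycle 1 DLT toward the MTD whether or not the drug is restarted. Later removal does not touch it.

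**The case against.** The strongest reply is that this is loose vocabulary. Section 5.8 is the dedicated follow-up section, 5.3 and the synopsis agree with it, and the schedule has its own follow-up column. Sections 5.5.3 and 5.5.4 govern dosing and do not mention ending follow-up. The literal reading would also clash with the safety assessment about 30 days after the last dose and with the monitoring of serious adverse events to resolution in Section 6.2. Disease evaluations are run from one centre whose investigators meet weekly, so divergent readings are unlikely. The affected endpoints are secondary and analysed descriptively.

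Most of this stands and is why the likely intent is removal from treatment. It does not settle the text: the literal instruction sits in the table that staff consult when a severe toxicity occurs, and nothing there points to 5.8.

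A reader might also infer more than the documents support:
- *That toxicity failures drop out of the analyses.* They would be censored at removal, not excluded.
- *That exactly the subjects who stop for toxicity are affected.* The 5.5.3 sentence covers every permanent stop, and Table 3 only three toxicity categories.
- *That survival at the MTD would be overstated by several points.* This needs an assumed poor survival in removed subjects, for which the documents give no figure, and it treats them as wholly excluded.
- *That following 5.8 as written removes the problem.* Its closing qualifier and footnote 8 leave room not to follow a non-responder who stops.

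**Conclusion.** The contradiction is real and stands in the current text. Section 5.5.3 and Table 3 can be read as ending participation when pomalidomide is stopped permanently, while 5.8, 5.3 and the synopsis require follow-up to progression and then for survival. The probable intent is removal from study treatment, but the protocol never says this.

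If the literal reading were applied, survival, response duration and time to worsening would be censored at treatment stop, which may be informative. No size or direction can be stated: the 20% and 77% used above are borrowed illustrations, survival after removal is unknown, and the bias is zero if removed subjects fare like the others or are in fact followed. For 18 subjects, the sampling error of about 10 points exceeds the shifts under the two assumed survival values. The case for acting is therefore that the ambiguity is avoidable at almost no cost, not that a bias has been shown. The DLT/MTD endpoint is unaffected.

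**What to change.** 1. In Section 5.5.3 and the Table 3 rows concerned, replace removal from study with *removed from study treatment and followed per Section 5.8*.
2. In Section 5.8, delete or define the closing qualifier, and reword schedule footnote 8 so that the three-monthly schedule is not confined to responders. Both should match follow-up of all subjects who stop treatment, apart from those who withdraw consent or cannot be reached.
3. In Section 10.3, add one sentence: stopping treatment is not in itself a censoring event for the survival and time-to-event summaries.

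The cost is a short wording amendment, with the sponsor review and IRB approval that Section 8.1 requires. Sections 5.3 and 5.8 already call for the follow-up, so extra contacts arise only where the qualifier or footnote 8 had been read narrowly. No dose, dose-modification step or clinical stopping rule changes.
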